**Table 1. Expected Precision for the Proportion of Treatment Patterns**

Expected Proportion of Treatment Pattern	Half-width of 95% CI for Proportion of Subjects with a Treatment Pattern			
	France (350 subjects)			
	Line 1 resectable (n=42)	Line 1 unresectable (n=168)	Line 2 resectable (n=140)	All subjects (n=350)
0.1	9.1%	4.5%	5.0%	3.1%
0.3	13.9%	6.9%	7.6%	4.8%
0.5	15.1%	7.6%	8.3%	5.2%

Expected Proportion of Treatment Pattern	Half-width of 95% CI for Proportion of Subjects with a Treatment Pattern			
	Germany (390 subjects)			
	Line 1 resectable (n=47)	Line 1 unresectable (n=187)	Line 2 resectable (n=172)	All subjects (n=390)
0.1	8.6%	4.3%	4.5%	3.0%
0.3	13.1%	6.6%	6.8%	4.5%
0.5	14.3%	7.2%	7.5%	5.0%

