### **5. STATISTICAL CONSIDERATIONS**

#### **5.1 Study Size**

This study will enrol approximately 740 subjects (up to 350 in France and up to 390 in Germany) in total. Enrolment into the study will be capped by country according to these numbers. Statistical properties of the study size are described in [Section 5.3](#). These samples sizes are consistent with previous submissions to reimbursement agencies.

---

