### 5.3 Sample Size Considerations

The analysis of this study will be descriptive in nature. Consequently, the sample size has not been assessed in terms of statistical power but with regards to what precision might be expected when examining categorical data such as type of anticancer therapy and discontinuation of Vectibix®. Proportions and confidence intervals will be most useful if reported in subgroups rather than overall. For instance the majority (perhaps 60%) of subjects recruited will be receiving first line treatment; their treatment patterns are expected to be different from second line subjects. Similarly, first line subjects with potentially resectable tumours (around 20%) will have different treatment patterns to those with unresectable tumours. Thus, we will have three important subgroups (the number of resectable subjects in the second line is expected to be negligible), consisting of 12% (line 1 potentially resectable), 48% (line 1 unresectable) and 40% (line 2) of the subjects in each country.

Table 1 below lists the expected precision of binomial estimates (in terms of half-width of a 95% confidence interval) using the planned sample sizes in the above scenarios. The expected precision in most of the subsets will be smaller than 10% but could be as high around 15% in Line 1 potentially resectable subjects.

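### Protocol Table 1 sizes the German second-line subgroup at 172 where Section 5.3's own split gives 156, so its printed precision is slightly too narrow and its column label is wrong (minor correction)

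*Protocol*

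**What the plan says.** Protocol Section 5.1 sets the planned enrolment at "up to 350 in France and up to 390 in Germany", about 740 in total. Section 5.3 explains that the size was examined through expected precision and not through power. It assumes that "the majority (perhaps 60%) of subjects recruited will be receiving first line treatment" and that around a fifth of those have potentially resectable tumours. This leads to three subgroups, "consisting of 12% (line 1 potentially resectable), 48% (line 1 unresectable) and 40% (line 2) of the subjects in each country". There is no separate resectable group in second line because "the number of resectable subjects in the second line is expected to be negligible".

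Table 1 is introduced as giving the "expected precision of binomial estimates (in terms of half-width of a 95% confidence interval) using the planned sample sizes in the above scenarios". Its German panel is headed "Germany (390 subjects" and has four columns: line 1 resectable (n=47), line 1 unresectable (n=187), "Line 2 resectable (n=172", and all subjects (n=390). Under the second-line column it prints 4.5%, 6.8% and 7.5% for expected proportions of 0.1, 0.3 and 0.5. The French panel uses 42, 168, 140 and 350, with the same *Line 2 resectable* label on its third column.

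**The concern.** Table 1 is meant to apply the Section 5.3 split to the planned country sizes. One of its six subgroup sizes does not follow from that split, and the German subgroups add to more than the German total shown in the same panel. A reader can find this by adding three numbers.

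The cell is one that will be used. Section 5.2.2 makes the second-line set (SLFAS) one of the two primary analysis sets, results are to be reported by country, and Section 5.3 says that subgroup proportions will be more useful than overall ones. German second line is therefore a planned reporting cell, and the protocol states its precision as slightly better than its own assumptions give.

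The label raises a second problem. Taken literally, Table 1 expects 140 resectable second-line subjects in France and 172 in Germany, while the text just above it expects hardly any.

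**Working it through.** **Inputs.** Country totals are 350 and 390 (Section 5.1 and the Table 1 panel headings). The subgroup shares are 12%, 48% and 40% in each country (Section 5.3). The precision measure is the half-width of a 95% confidence interval for a binomial proportion (Section 5.3), evaluated at p = 0.1, 0.3 and 0.5 (Table 1).

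**Step 1: subgroup sizes** (share × country total).

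| Country | 12% | 48% | 40% | Sum of printed sizes |
|---|---|---|---|---|
| France, 350 | 42.0 (printed 42) | 168.0 (printed 168) | 140.0 (printed 140) | 42 + 168 + 140 = 350 |
| Germany, 390 | 46.8 (printed 47) | 187.2 (printed 187) | 156.0 (printed **172**) | 47 + 187 + 172 = **406** |

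Five of the six sizes agree. The German second-line figure is 172 − 156 = 16 too large, about 10% of 156. As a share, 172/390 = 44.1% and not 40%. With 156 the panel closes: 47 + 187 + 156 = 390. Rounding cannot explain a gap of 16.

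**Step 2: the method behind the printed half-widths.** Table 1 does not name its interval. The Wald formula, half-width = 1.96 × √(p(1 − p)/n), reproduces every printed half-width in both panels at the printed n. The smallest column shows that alternatives do not fit: at n=42 and p=0.5, Wald gives 15.1% as printed, Wilson gives 14.5%, and a continuity-corrected interval gives 16.3%.

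**Step 3: the German second-line column.**

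| p | Printed | Wald, n=172 | Wald, n=156 | Difference, 156 minus 172 |
|---|---|---|---|---|
| 0.1 | 4.5% | 4.483% | 4.708% (4.7%) | 0.22 points |
| 0.3 | 6.8% | 6.848% | 7.191% (7.2%) | 0.34 points |
| 0.5 | 7.5% | 7.472% | 7.846% (7.8%) | 0.37 points |

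For example, at p = 0.5: 1.96 × √(0.25/172) = 7.47% and 1.96 × √(0.25/156) = 7.85%; to three decimals the latter is 7.846%, so it prints as 7.8%.

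The printed values match n=172. The wrong size was therefore carried into the results, and this is more than a misprint in the column header.

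**Step 4: the label.** Section 5.3 defines the 40% group as line 2 without further division and says why it is not divided. The French 140 is exactly 40% of 350, so the column holds all second-line subjects. The word *resectable* in its heading contradicts the text in both panels.

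**The case against.** The strongest reply is that nothing depends on this figure. The study is descriptive, with no hypothesis test and no power claim, and the protocol sets no precision threshold that 7.8% would miss. Section 5.3 concludes only that half-widths are under 10% in most subsets and may reach about 15% in first-line potentially resectable subjects. That is equally true at n=156. The corrected German column is still tighter than the French second-line column (5.0%, 7.6%, 8.3% at n=140). This part of the reply stands, and it makes the point minor.

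It can also be said that the inputs are soft. The 60% first-line share is given as approximate and the country sizes are upper limits. As an illustration under assumed shares, first-line proportions of 55% and 65% would give 0.45 × 390 = 175.5 and 0.35 × 390 = 136.5 German second-line subjects, about 176 and 137. At p=0.5 the half-widths would be 0.98/√176 = 7.4% and 0.98/√137 = 8.4%. That range is wider than the error. It shows that neither 156 nor 172 predicts what recruitment will deliver. It does not rescue 172, because the table says it uses the stated scenario and in this one column it does not.

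A reader might infer more than the protocol supports:

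- **That the sample size rests on this table alone.** Section 5.1 gives a second basis, agreement with earlier reimbursement submissions.
- **That Germany could enrol 406.** The cap of 390 is stated in the synopsis and in Sections 3.2 and 5.1, and Table 1 itself prints 390 twice.
- **That 172 is left over from a different planned total.** It would be 40% of 430, but no such total appears in the protocol, so its origin is unknown.
- **That the table is deficient because it shows all subjects and has no column for the whole first-line set (FLFAS).** The protocol promises precision for three subgroups and supplies it. Further columns would be a preference and would correct no error.

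**Conclusion.** The error is definite and small. Under the protocol's own split and country total, German second line is 156 and not 172, and the three half-widths should read 4.7%, 7.2% and 7.8% where the table has 4.5%, 6.8% and 7.5%. The *resectable* label is wrong in both panels.

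This rests on two assumptions: that the 12/48/40 split applies to Germany, as Section 5.3 says for each country, and that the table uses Wald intervals, as all its other half-widths show. The size error of 156 against 172 does not depend on the second assumption.

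The general statement on precision, the country caps, the total of 740, the analysis sets and the methods are all unaffected. This is a minor correction to the precision table and gives no reason to change the design.

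**What to change.** In Protocol Table 1, German panel, replace n=172 by n=156 and print 4.7%, 7.2% and 7.8% at expected proportions 0.1, 0.3 and 0.5. In both country panels rename the column *Line 2 (all)*. The concluding text of Section 5.3 can stay as it is.

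If the sponsor did mean 172, the German split has to be restated so that the subgroups add to 390. The 40% share, the total of 390 and n=172 cannot all hold.

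The cost is a text edit in one table. The stated precision becomes slightly less favourable, and nothing changes in enrolment, data collection or analysis.

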#### 5.4 Access to Individual Subject Treatment Assignments by Amgen or Designees

Randomization and unblinding procedures are not applicable to this study design.

#### 5.5 Interim Analysis and Early Stopping Guidelines

No interim analysis is planned. Early stopping rules will not be applied due to the observational nature of this research program.

#### 5.6 Planned Methods of Analysis

##### 5.6.1 General Approach/Considerations

The analysis of this study will be descriptive in nature. The data will be summarized for subjects with metastatic colorectal cancer (mCRC) with tumour expressing wild-type (non-mutated) *KRAS* who received Vectibix® in combination with FOLFOX as first-line

---

treatment and subjects who received Vectibix® in combination with FOLFIRI as second-line treatment and received first-line fluoropyrimidine-based chemotherapy (excluding irinotecan). The data will be summarized by country to fulfil local post reimbursement requirements. For continuous outcomes, the mean, standard deviation, median, and range will be provided. For categorical variables, the frequency and percentage, with two-sided 95% CI, will be displayed for the treatment pattern of Vectibix®. Summary tables and analyses will be based on FLFAS and SLFAS and corresponding local tumour response analysis sets.

For each outcome parameter, the covariates listed in [Section 5.2.3](#) will be assessed in a logistic or general linear model. Non-significant factors will be eliminated stepwise until only covariates significant at the 5% level remain, thereby indicating which covariates have an important influence on treatment pattern. Summary statistics will then be reported for each level of the significant covariates.

Selected sensitivity analyses may be performed to assess the impact of protocol deviations using other analysis sets.

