### **2.2.1 Vectibix® (Panitumumab) Clinical Experience in mCRC – Safety**

The clinical safety profile of panitumumab as monotherapy and in combination with chemotherapy is based on results from clinical studies in subjects with a variety of solid tumours. These studies indicated that panitumumab is generally well tolerated. Twenty of these studies involved subjects with mCRC (n = 2588 receiving panitumumab as a single agent or in combination). In these subjects, dermatologic-related toxicities were the most frequently reported adverse events (93% of subjects), with most events being mild to moderate. Relatively few subjects (2%) permanently discontinued panitumumab due to dermatologic adverse events. Infusion reactions to panitumumab (defined as any reported allergic reaction, anaphylactoid reaction, chills, fever, or dyspnoea, occurring within 24 hours of the first dose that were not otherwise designated as either anaphylactoid or allergic reaction) were infrequent (3% of subjects; < 1% serious); premedication was not mandated in study protocols. Panitumumab immunogenicity, as measured by enzyme-linked immunosorbent assay (ELISA) and Biacore assay, was very low. Compared with subjects who did not develop antibodies, no relationship

between the presence of anti-panitumumab antibodies and the safety of panitumumab was observed, although the small sample size limits these analyses.

In an analysis of 4 mCRC monotherapy studies (20020408, 20030194, 20030167, and 20030250), no significant differences in the adverse event profile of panitumumab were observed between subjects with wild-type *KRAS* and subjects with mutant *KRAS* when adjusted for duration of exposure.

The clinical safety profile of panitumumab in combination with chemotherapy is based on results from 9 clinical studies with data from 1536 subjects, including 585 subjects who received panitumumab in combination with oxaliplatin-based chemotherapy and 951 subjects who received panitumumab in combination with irinotecan-based chemotherapy. These data primarily consist of results from Studies 20050203 and 20050181.

The safety results of the two pivotal studies (20050203, first-line treatment with oxaliplatin and 20050181, second-line treatment with irinotecan) indicate a tolerable safety profile for panitumumab when administered in combination with chemotherapy to subjects with wild-type *KRAS* mCRC as initial and second-line therapy.

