### 5.2.3 Covariates

Certain pre-treatment factors (covariates) may be found to affect the pattern of Vectibix® usage, hence subgroup analysis will be used to investigate the covariates listed below with a view to a numerical evaluation of their influence.

The following covariates may be used to conduct the subgroup analyses for all subjects:

- ECOG performance status: ≤1 vs. 2
- Location of primary tumour: colon vs. rectum, right or left
- Number of sites of metastatic lesions: 1 vs. 2 vs. ≥3 and per organ (liver, lung, other etc)
- Location of sites of metastatic disease: liver only vs. other sites ± liver
- Prior adjuvant therapy: yes vs. no (regimen and date last adjuvant treatment administered)
- Type of centre
- Individual treatment goals (including resectability)
- The following covariates may be used to conduct the subgroup analyses for SLFAS:
- Categories of prior systemic therapy mCRC: chemotherapy only vs. chemotherapy plus targeted therapy
- Prior anti-EGFR therapy for mCRC : yes vs. no
- Prior anti-VEGF therapy for mCRC: yes vs. no
- Prior oxaliplatin-based chemotherapy for mCRC: yes vs. no
- Prior irinotecan-based chemotherapy for mCRC: yes vs. no

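### For uncommon treatment patterns, the stepwise logistic models start with about 13 parameters and 1 to 2 events per parameter, so surviving elimination does not show important influence

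*Protocol*

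**What the plan says.** Section 5.6.1 says that, for each outcome, the covariates of Section 5.2.3 will be assessed in a logistic or general linear model. It continues: "Non-significant factors will be eliminated stepwise until only covariates significant at the 5% level remain". The survivors are taken to have an important influence on treatment pattern, and summary statistics are then given for each of their levels.

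Section 5.2.3 is more permissive: "The following covariates may be used to conduct the subgroup analyses for all subjects", with five further covariates for the second-line set. Section 5.3 sizes the study for the precision of single proportions only. It splits enrolment into subgroups "consisting of 12% (line 1 potentially resectable), 48% (line 1 unresectable) and 40% (line 2) of the subjects in each country".

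The protocol does not name the test used for elimination, does not say whether the models are fitted by country or pooled, and sets no minimum number of events.

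**The concern.** The sample size was chosen for estimating one proportion at a time. The same data are then asked to support a multi-covariate model with data-driven selection, and the survivors are given a substantive meaning. For an uncommon pattern two things can go wrong.

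First, some covariate level may contain no events, or a combination of covariates may separate events from non-events. The maximum-likelihood estimate then does not exist, and any p-value from the fit depends heavily on which test is used. Second, repeated testing at 5% leaves survivors even when nothing is related to the outcome.

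At stake is what is said about which patients have dose reductions, delays or discontinuation. These are primary outcomes, and Section 2.3 says the data are meant for reimbursement agencies. The level-wise tables that Section 5.6.1 promises also depend on which covariates survive.

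**Working it through.** **The plan's own figure.** Table 1's half-width is 1.96 × √(p(1−p)/n). For n = 140 and p = 0.1 this is 1.96 × √(0.09/140) = 4.97%, printed as 5.0%. All 24 cells reproduce at the printed n. Table 1 therefore concerns single proportions only.

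**Sizes.** Section 5.1: "This study will enrol approximately 740 subjects (up to 350 in France and up to 390 in Germany) in total". With Section 5.3's shares, first line is 60% (210 France, 234 Germany, 444 together) and second line is 40% (140, 156, 296). Table 1 prints "Line 2 resectable (n=172" for Germany, but 40% of 390 is 156, and 47 + 187 + 172 = 406, not 390. At 172 there would be 17.2 events, and 31.2 pooled, which changes nothing below.

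**Parameters.** From Section 5.2.3, each factor coded once:
- Common to both lines: ECOG 1, primary location and side 2, number of sites 2, liver-only 1, adjuvant therapy 1, type of centre 3 (four types named in Section 3.1). Sum 10.
- First line: treatment goals 3 (four goals in the Glossary). Total 13, or 16 with three per-organ terms.
- Second line: prior anti-EGFR, anti-VEGF and oxaliplatin, 3. Total 13. Prior irinotecan is left out because the second-line set excludes it by definition. The chemotherapy-versus-targeted category largely repeats the anti-EGFR and anti-VEGF terms. Counting all five terms and the goals gives 10 + 5 + 3 = 18.

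**Events and separation.** Events = n × 0.1, divided by 13 for events per parameter. The last column is the simulated share of full 13-parameter models with no finite estimate: 300 data sets per cell, independent covariates, no covariate effects, separation detected by linear programming. The protocol gives no covariate prevalences, so three assumed sets were used: balanced; intermediate (ECOG 2 at 10%, rarest centre type and goal at 10%, prior anti-EGFR at 5%); and the intermediate set with ECOG 2 at 5%.

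| Set | n | Events | Per parameter | No finite estimate |
|---|---|---|---|---|
| Second line, France | 140 | 14 | 1.1 | 27 / 75 / 83% |
| Second line, Germany | 156 | 15.6 | 1.2 | 14 / 64 / 78% |
| Second line, pooled | 296 | 29.6 | 2.3 | 0.3 / 30 / 43% |
| First line, France | 210 | 21 | 1.6 | 5 / 28 / 53% |
| First line, Germany | 234 | 23.4 | 1.8 | 3 / 24 / 45% |
| First line, pooled | 444 | 44.4 | 3.4 | 0.3 / 3 / 11% |

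A further simulation under other assumed prevalences gave about 41, 33, 6, 20 and 20% for the first five rows and 1% or less for the last, inside these ranges. At 0.3 the share is 0-28%, mostly under 12%. At 0.5 it is at most 9%.

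A hand check: if a level has prevalence q, the chance that none of D events falls in it is about (1−q)^D. For q = 0.05 this is 0.95^14 = 49% with 14 events and 0.95^44 = 10% with 44. For q = 0.10 it is 0.90^14 = 23% and 0.90^44 = 1%. One uncommon level can account for much of the problem.

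**Elimination, by test.** One level with 20% prevalence was given an event rate of 0.5% and the overall rate was 0.1, with 150 runs each at n = 140, 210, 296 and 444. Wald elimination kept the covariate in 0, 3, 23 and 47 runs. Likelihood-ratio elimination kept it in 127, 137, 149 and 150. In the runs where the level had no events at all, Wald kept it in none, at any n. In the further simulation, a covariate with a zero-event level was kept in 0% of runs by Wald, 93-100% by likelihood ratio and 72-100% by Firth penalised likelihood.

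**Selection with no true effects.** Under the intermediate prevalences at 0.1, at least one covariate survived in 16-26% of runs with Wald tests and 25-43% with likelihood-ratio tests. At 0.3 the figures were 24-34% and 27-42%. This comes from repeated testing and does not disappear when events are more frequent: eight independent tests at 5% give 1 − 0.95^8 = 34%.

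**The case against.** Much of the case on the other side stands.

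- A reader might infer that the rule discards the strongest covariates. The protocol does not support that as stated, because it names no test. The loss is a property of Wald p-values and largely disappears with likelihood-ratio tests. The SAP, not shown, may settle this.
- A reader might infer that these logistic models generally cannot be fitted. That is too broad. 0.1 is the lowest of three proportions in Table 1, pooled first line has 44 events, and Section 5.6.1 requires summaries by country but does not say that the models are fitted by country. The separation rates also rest on prevalences that the protocol does not give.
- A reader might apply the point to even rarer outcomes, citing Section 2.2.1: "Relatively few subjects (2%) permanently discontinued panitumumab due to dermatologic adverse events". That figure comes from earlier studies that included monotherapy. Section 5.6.2.1 says that discontinuation reasons will be summarised and specifies no separate model for each reason.
- Cumulative dose, maximum dose, duration and number of infusions would use general linear models, which are unaffected. Summaries by line and country, and response by treatment goal, are reported whatever survives.
- A minimum of 10 events per parameter, with covariates tested singly below it, may look like the natural remedy. It is a debatable rule of thumb, gives up mutual adjustment and does not reduce false selection.

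What remains is that Section 5.6.1 itself fixes elimination at 5% and the meaning given to survivors. The permissive wording in Section 5.2.3 does not undo that. No choice of test adds events, makes a separated maximum-likelihood estimate finite, or removes false selection.

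**Conclusion.** The point holds for binary outcomes near Table 1's lowest proportion, in second line and in first line by country. There the models have 14 to 30 events for about 13 parameters. The maximum-likelihood estimate may fail to exist in 14-83% of second-line country models, 3-53% of first-line country models and 0.3-43% of pooled second-line models. The width of these ranges reflects the unknown covariate prevalences. If Wald p-values are used, a covariate level with no events was dropped in every simulated run.

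Separately, the 16-43% selection rate with no true effects means that survival of this procedure cannot be read as important influence, whichever of the two tests is used. The event counts and the parameter count follow from the protocol. The separation and selection rates are simulated under stated assumptions. The main descriptive estimates of treatment pattern are not affected.

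**What to change.** In Section 5.6.1:

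1. For binary outcomes, use Firth-penalised logistic regression, with penalised-likelihood tests for elimination and penalised-likelihood 95% confidence intervals, and not Wald p-values. Estimates stay finite under separation and mutual adjustment is kept.
2. Omit prior irinotecan from the second-line models, where it is constant by the definition of the set.
3. Replace the clause that reads survivors as influential with a statement that the selection is exploratory. Report level-wise summaries for all covariates listed in Section 5.2.3, not only those retained. This part is needed because penalisation does not cure false selection.

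The cost is a change of wording here and in the SAP, a standard software option, slightly more output and a weaker stated conclusion. No design change or additional data are needed.
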